A randomized trial evaluating single fraction stereotactic versus standard multi-fraction radiotherapy for patients diagnosed with bone metastases for effective palliation of symptoms.

1. OBJECTIVES:

- a. Primary objective (phase II): evaluate single fraction stereotactic regimen for pain response in terms of time to failure, defined as the first occurrence of any of the following events:
 - i. worsening in pain score by at least 2 categories by MDASI survey,
- b. Primary objective (phase III): to evaluate the pain response at 3 months in terms of pain response by a decrease in 2 categories by MDASI survey and narcotics use as defined by international pain consensus criteria.
- c. Secondary objective: report outcomes
 - i. Compare narcotics/opioid use compared to baseline, $\geq 50\%$ increase in dose of opioid/narcotic medication,
 - ii. re-irradiation,
 - iii. radiographic disease progression or development of pathologic fracture from disease progression
 - iv. Prospectively report pain, quality of life, and symptoms using MDASI assessment tool to measure pain response
 - v. Report acute (skin, fatigue, flare reaction) and long term (sclerosis, bone ossification, bone fracture rate) toxicity associated with treatment.
 - vi. Report local control and overall survival
 - vii. Report rate of salvage surgery

2. BACKGROUND:

- a. Radiation therapy is commonly utilized to effectively palliate symptomatic bone metastases, 50%-80% of patients experience improvement in the pain and 20%-50% report complete pain relief (1, 2). However, the optimal fractionation scheme to produce durable pain relief is still being studied. Historically, clinical trials have compared efficacy of varying dose-fractionation in alleviating symptoms. Ratanatharathorn et al. concluded in their analysis that higher dose fractionated treatments produced better pain outcomes compared to lower-dose regimens (3, Ratanatharathorn). Contrary to this, McQuay et al. in their summary determined no difference in efficacy between different fractionation or dose response in the total dose delivered for painful bone metastases (4, McQuay). In the meta-analysis performed by Wu et al (5, Wu) the authors compared pain relief among various dose-fractionation schedules of localized radiotherapy (RT) in the treatment of painful bone metastases. They concluded among the randomized trials, there was no significant difference in overall pain

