 - c. After start of treatment, all patients will be followed by phone calls within 7-14 days, and at + 1 month (+/- 1 week) and then with clinic visits at months 3, 6, 9, 12 (+/- 4 weeks for each visit) and every 3 to 6 month intervals thereafter (until death) by either the radiation oncology or orthopedic team to evaluate toxicity. The validated surveys (MDASI) will be completed at baseline prior to radiation and at each follow up interval/appointments. The patient medical record number will be placed on the survey before it is given to the patient for completion. The surveys may be filled out in person or by mail.
 - d. Patients will report their symptom measures with validated quality of life instrument MDASI index. The M.D. Anderson Symptom Inventory (MDASI) is a multi-symptom patient reported outcome measure evaluating 13 core symptom items interfering with patients' daily life (Appendix B).
 - e. We will also prospectively report the narcotics/NSAIDs utilization and outcome at each follow-up interval after radiation therapy.
8. EVALUATION OF TOXICITY:
- a. During radiotherapy, the patient will be examined weekly and acute reactions recorded.
 - b. Toxicity occurring after 3 months of radiation therapy; these will be evaluated and documented using NCI CTCAE version 4.03 (Appendix A).
9. CRITERIA FOR RESPONSE:
- a. The response to treatment will be determined by both radiographic scans and symptoms reported.
 - b. Complete pain relief is defined as average pain score of 0 for two consecutive analysis periods.
 - c. The time to maximal relief of pain is defined from the first day of irradiation until the lowest pain score after radiation therapy.

- d. Treatment failure is defined as worsening of pain by at least two categories, >50% increase in dose of opioid/narcotic medications, re-irradiation for pain or disease progression, progression or development of pathologic fracture from disease progression.
 - e. Any patient with progressive pain in the radiated area will have work up which include radiographic scans to evaluate for bone stability and pathologic fracture per standard of care.
10. RE-TREATMENT:
- a. Response and pain relief from radiation therapy may take several weeks; therefore patients should not be re-irradiated for at least 4 weeks after completion of radiation. Dose and fractionation are left to the discretion of the treating radiation oncologist.

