 - b. Surgical intervention for treatment failures, bone instability, or fractures will be reported.

11. STATISTICAL CONSIDERATIONS:

This is a phase II/III non-inferiority trial following the design suggestions of Korn et al. (14, Korn). The primary outcome for phase II part is treatment failure at 1 month, where treatment failure is as defined in section 1.0. We assume that time to treatment failure follows an exponential distribution for each treatment arm (standard radiation, hypofractionated radiation). We also assume that the standard radiation arm will have 25% of patients with treatment failure at 3 months, based on the study by the Bone Pain Trial Working Party (15, BPTWP). A hazard ratio of 1.5 implies that the hypofractionated radiation arm will have 35% of patients with treatment failure at 3 months. The primary outcome for phase III part is pain response rate at 3 months post randomization. We expect to enroll 10 patients per month.

Randomization

Patients will be randomized to standard or single fraction stereotactic radiation therapy using CORE. Randomization will be stratified by tumor size (≤ 4 cm vs. > 4 cm), site of bony mets (extremities, pelvis, abdomen, head/neck, chest), and 1 vs >1 site irradiated. We expect approximately 40% of patients will have bony mets in the extremities and approximately 35% will have bony mets in the pelvis. We expect the distribution of patients enrolling will approximately be 40% lung malignancy, 25% genitourinary malignancy, 15% breast malignancy, 10% multiple myeloma and 10% other malignancy. We will have a total of 14 stratification levels.

Phase II

We will test the following hypothesis:

$$H_0: \rho = 1.5 \quad \text{vs.} \quad H_1: \rho = 1.0,$$

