where ρ is the hazard ratio (hypofractionated/standard) for time to treatment failure, as defined in section 1.0. A sample size of 150 patients (75 randomized to each treatment arm) will yield 90% power with a 1-sided significance level of 0.20 to reject the null hypothesis (H_0) and conclude that hypofractionated treatment is not inferior to standard treatment in terms of time to treatment failure. We use a 1-sided significance level of 0.20 as recommended by Rubinstein et al. (16, Rubinstein) for phase II screening trials. This sample size will yield 110 events (i.e., treatment failures). It will take 15 months to enroll all the patients, and the maximum study duration is expected to be 22 months to observe the 110 events. The final analysis for phase II will be performed once we've observed 110 events, and we will suspend accrual while we wait for these events to occur. We will continue to phase III only if we reject H_0 at the 0.20 significance level.

Phase III

The patients enrolled in the phase III part of the study will be included in the phase III part of the study. In the Phase II trial, we have already enrolled and randomized 160 patients, therefore we are requesting to enroll another additional 50 patients to reach a total of 210 patients. We will enroll another 50 patients in total of 210 patients (105 randomized to each treatment arm), after the rejection of the H_0 in the phase II part of the trial. The primary objective is to evaluate the pain response at 3 months by international pain consensus criteria after the additional 50 patients have been accrued, we will follow all patients for at least 3 months to assess the pain response. Assuming a 20% of the 3-month pain response rate for patients on MFRT arm, the 210 patients will ensure an 80% power to detect a 16% improvement in response rate (36%) with SBRT using a 1-sided 5% level test.

Pain response at 3 months is defined as reduction in pain score reported by MDASI at 2 points below baseline also taking into account narcotics use, as defined by International Pain Response Criteria.

This sample size calculation was performed using East 6 (Copyright © 2010, Cytel Inc., Cambridge, MA).

Toxicity Monitoring (phase II and phase III)

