At any point in the trial time to radiation induced toxicity can be calculated for each patient, with the time interval regarded as censored at the date of last follow-up if toxicity has not been observed for a patient. We will apply a Bayesian method for updating prior information with time to toxicity data observed to that time. We assume that the time to toxicity for each patient is exponentially distributed with a median of λ_S months for the standard treatment and a median of λ_E for the experimental treatment. Given the historical data we assume λ_S follows an inverse gamma distribution with mean 78.95 months and a standard deviation of 0.15 months. The middle 95% of this distribution is between 78.66 and 79.24 months. These parameters correspond to a 12-month toxicity rate between 9.064% and 10.035%. We assume λ_E follows an inverse gamma distribution with a mean of 78.95 months and a standard deviation of 15.0 months. The middle 95% of this distribution is between 54.87 and 113.32 months. These parameters correspond to a 12-month toxicity rate between 7.077% and 14.066%.

Since the goal of the study is to achieve a toxicity rate of less than 10% at 12 months, the trial will be stopped early if, based on the available data, $\Pr(\lambda_E < \lambda_S \mid \text{data from the trial}) > 0.90$. This rule was chosen to achieve an approximately 0.10 early stopping probability if the true toxicity rate is 10%.

Final Analysis

We will use descriptive statistics to summarize the demographic and clinical characteristics of patients by treatment arm.

We will use the methods of Gooley et al. (18, Gooley) to estimate the cumulative incidence of treatment failure for each treatment arm with death as a competing event, and we will estimate the percent of patients without treatment failure at 3, 6, and 12 months for each treatment arm with a 90% confidence interval.

We will use the methods of Fine and Gray (19, Fine and Gray) to model time to treatment failure with death as a competing event and test the hypotheses stated above for phase II and for phase III. We will also estimate the hazard ratio for treatment with a 90% confidence interval.

For the 3 month pain response rate, the Cochran-Mantel-Haenszel test stratified by stratification factors at randomization will be used to test the difference between 2 treatment arms. Chi-squared test without adjusting for the stratification factors will also be performed as a secondary analysis.

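### The phase II endpoint that gates phase III is stated two ways twice over: failure at 1 month or time to failure, and pain worsening alone or a composite

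*Combined protocol and SAP*

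**What the plan says.** **Time frame.** The opening of section 11 says "The primary outcome for phase II part is treatment failure at 1 month, where treatment failure is as defined in section 1.0". Section 1.a instead describes "time to failure, defined as the first occurrence of any of the following events". Section 11, Phase II, tests a parameter that "is the hazard ratio (hypofractionated/standard) for time to treatment failure, as defined in section 1.0", with a null value of 1.5 and an alternative of 1.0, and analyses at 110 events. Section 11, Final Analysis, uses Fine-Gray regression to "model time to treatment failure with death as a competing event and test the hypotheses stated above for phase II".

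**Event list.** Section 11 refers twice to section 1.0 for the definition. There, section 1.a announces several events but lists one: "worsening in pain score by at least 2 categories by MDASI survey". Opioid increase, re-irradiation and "radiographic disease progression or development of pathologic fracture from disease progression" appear in section 1.c as secondary objectives. Section 9.d uses the same term differently: "Treatment failure is defined as worsening of pain by at least two categories, >50% increase in dose of opioid/narcotic medications, re-irradiation", followed by progression and pathologic fracture.

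**Consequence of the test.** Section 11, Phase II: "We will continue to phase III only if we reject H_0 at the 0.20 significance level". The Phase III paragraph adds that 160 patients have already been randomized.

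**The concern.** A go/no-go test needs one endpoint, and this text supports more than one. A reader who starts from the sentence naming the primary outcome finds a 1-month endpoint; one who starts from the hypothesis finds an unrestricted time-to-event endpoint. On events, an analyst could count pain worsening alone and cite section 1.a, or count the composite and cite section 9.d.

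The two lists could give different hazard ratios. Section 2 reports that in the cited trial of 8 Gy in one fraction against 30 Gy in ten, pain and narcotic relief were equivalent but re-treatment was more frequent after the single fraction. Re-irradiation counts as failure under 9.d and not under 1.a. That shows only that the lists could diverge by arm. This trial uses higher single doses (12 or 16 Gy, section 6), and another trial cited in section 2 found time to failure itself inferior after a single fraction.

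The documents do not say whether the gate has been analysed, or under which list. With 160 patients randomized, an unsettled definition leaves room to choose after seeing data.

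**Working it through.** **Inputs (section 11).** Null hazard ratio (HR) 1.5, alternative 1.0; one-sided alpha 0.20; power 90%; 150 patients, 1:1; 15 months of accrual; analysis at about 22 months; exponential failure times with 25% failure at 3 months on standard. No phase II dropout is stated; none is assumed, and deaths are ignored.

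**1. Reproduce the plan's figures as a time-to-event design.**
- Events: 4 × (0.8416 + 1.2816)² / (ln 1.5)² = 109.7, so 110. Power at 110 events is 0.9005.
- Hazard: λ = −ln(0.75)/3 = 0.0959 per month. At HR 1.5, 3-month failure is 1 − exp(−1.5 × 3 × 0.0959) = 35.0%, as stated.
- Expected events at month 22 under HR 1.0: 150 × [1 − (exp(−7λ) − exp(−22λ)) / (15λ)] = 109.4.

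Events, power and duration all reproduce for time to failure without a 1-month limit.

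**2. Take 1 month literally.**
- Risk at 1 month: 1 − exp(−0.0959) = 9.14% on standard, and 13.4% at HR 1.5.
- Failures in 150 patients: 150 × 0.0914 = 13.7 at HR 1.0; 75 × 0.0914 + 75 × 0.134 = 16.9 at HR 1.5.
- Power with 75 per arm and the same margin is about 52% as a difference in proportions, or about 46% by the Schoenfeld formula on about 14 events. About 414 per arm would be needed for 90%.

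The stated sizing cannot belong to a 1-month endpoint.

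**3. How the event list affects the gate.** Passing requires an observed HR below exp(ln 1.5 − 0.8416 × 2/√110) = 1.278. With 110 events and a true HR of 1.0, power is 90% under either list.

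Let q be the share of standard-arm first failures that come from the added components. Then composite HR = (1 − q) × HR(pain) + q × HR(added), and pass probability = Φ[(ln 1.5 − ln HR) × √110/2 − 0.8416]. The documents give neither q nor component HRs; all values below are assumptions.

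| HR, pain worsening | HR, added | q | Composite HR | Pass probability, pain alone | Pass probability, composite |
|---|---|---|---|---|---|
| 1.0 | 2.0 (re-irradiation only) | 0.05 | 1.05 | 0.90 | 0.848 |
| 1.0 | 2.0 (re-irradiation only) | 0.10 | 1.10 | 0.90 | 0.784 |
| 1.0 | 1.5 (re-irradiation only) | 0.05 | 1.025 | 0.90 | 0.876 |
| 1.0 | 1.5 (re-irradiation only) | 0.10 | 1.05 | 0.90 | 0.848 |
| 1.2 | 1.0 | 0.10 | 1.18 | 0.629 | 0.662 |
| 1.2 | 1.0 | 0.30 | 1.14 | 0.629 | 0.725 |

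With pain worsening at HR 1.0 and re-irradiation at HR 2.0, the pass probability reaches 50% only when q = (1.278 − 1)/(2.0 − 1) = 0.278. If every component has HR 1.0, the list makes no difference.

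**4. How the event list affects timing.** The plan does not say which definition the 25% at 3 months refers to. If pain worsening alone gave 10%, 15% or 20% (assumed), the formula in step 1 gives about 59, 80 or 96 events at month 22, and 110 events at about month 46, 33 or 26.

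**The case against.** The strongest reply is that the text already resolves both points. Everything operative in section 11 specifies time to failure, so nobody could run the stated test on a 1-month proportion. That is right, and it makes the 1-month phrase a wording correction with no effect on the analysis.

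For the event list, section 11 points to section 1.0 and never to 9.d, and section 1 has a readable hierarchy: pain worsening primary, the rest secondary. On that reading 1.a governs and 9.d was simply not aligned. This makes 1.a the better-supported reading but does not settle the matter. The list in 1.a promises several events and stops after one that ends in a comma, and 9.d gives an explicit definition of the identical term.

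Two further limits stand. Phase III has its own endpoint and its own one-sided 5% test, and an extra condition passed beforehand cannot raise its false-positive rate. The harm is therefore confined to the go/no-go decision and the phase II non-inferiority claim. Also, the component figures are assumed, the ranges of q differ between the adverse and favourable cases, and the formula ignores deaths although the planned test treats death as a competing event. The figures show that the list can matter; they do not estimate how much it will.

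**Conclusion.** The concern holds, with high confidence, and must be fixed. The 1-month wording is a misstatement: it implies about 14 events where the design needs 110. The double definition of treatment failure is the substantive fault, because it contradicts itself on which hazard ratio is tested at a stated gate.

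Its size cannot be determined from the documents. Under the assumptions tabulated, using the composite instead of pain worsening moves the pass probability from 90% down to as little as 78%, or from 63% up to 66-72%; with equal arms on every component it does not move. The margin, alpha, 110 events and decision rule are stated, reproduce, and are not in question.

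**What to change.** - In section 11, replace the 1-month wording with time to treatment failure.
- Reconcile sections 1.a, 1.c and 9.d to one event list. Align the opioid threshold as well: 1.c.i sets it at 50% or more, 9.d at more than 50%.
- State which definition the 25% failure at 3 months refers to.
- Record in a dated note which definition was or will be applied at the phase II gate, and when it was fixed.
- Report the gate result under the other definition as a sensitivity analysis, with first-event counts by component and arm.

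The cost is protocol wording, the note and one extra analysis. Before running the composite, confirm that dates of re-irradiation and the other events are recorded. Section 11, Final Analysis, plans to compare re-irradiation rates, but neither schedule in section 14 has a column for re-irradiation. That does not prove the data are missing, but it should be checked.

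### Phase II projects 110 failures by month 22 with no allowance for death or loss before failure, and only the 110th failure triggers its analysis

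*Combined protocol and SAP*

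**What the plan says.** Section 11 sets the phase II test as hazard ratio 1.5 (null) against 1.0, one-sided level 0.20, 90% power, with 150 patients at 10 per month over 15 months. On timing: "We assume that time to treatment failure follows an exponential distribution for each treatment arm", with 25% failing by 3 months on the standard arm, and "the maximum study duration is expected to be 22 months to observe the 110 events". The analysis runs once 110 failures have been seen; until then "we will suspend accrual while we wait for these events to occur". The gate is explicit: "We will continue to phase III only if we reject H_0 at the 0.20 significance level".

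The Phase III paragraph adds "In the Phase II trial, we have already enrolled and randomized 160 patients" and requests 50 more, to be enrolled "after the rejection of the H_0 in the phase II part of the trial". It does not say whether 110 failures were reached or whether the test was run.

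Section 9 begins "Treatment failure is defined as worsening of pain by at least two categories" and goes on to opioid increase, re-irradiation, progression and fracture. Section 1 lists only the pain component for phase II. Neither includes death. The Final Analysis part of Section 11 treats death as a competing event and applies a Fine-Gray model to the phase II hypothesis. The sample-size text gives no rate of death, dropout or loss. The only statement on survival is the eligibility criterion in Section 4 of a life expectancy above 3 months.

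**The concern.** A patient who dies or is lost before failing can never count toward the 110. Deaths after a failure cost nothing. The analysis plan recognises death as a competing event, but the event projection does not appear to. If the 22-month figure holds only with no such losses, the stated duration is too short. If losses are heavy enough, 110 failures may never occur among the phase II patients.

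The failure count is the only trigger for the analysis that opens phase III, accrual is suspended while waiting, and no calendar alternative is given. The main risk is therefore an open-ended wait. An earlier analysis with fewer failures would leave the 0.20 level intact and reduce power.

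**Working it through.** **Inputs from Section 11.** Margin 1.5, alternative 1.0, one-sided 0.20, power 0.90, 1:1 allocation, 10 patients per month, 25% failure at 3 months, exponential failure times. Accrual window *a* is 15 months for 150 patients and 16 months for 160 at the planned rate.

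**1. The plan's event count.** Required events = 4 × (1.2816 + 0.8416)² / (ln 1.5)² = 109.7, so 110. This reproduces.

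**2. The plan's timing.** The failure hazard is λ = −ln(0.75)/3 = 0.0959 per month. Let m be the hazard of death or loss before failure and h = λ + m. The expected fraction failed by month T is

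(λ/h) × [1 − (e^(−h(T−a)) − e^(−hT)) / (h·a)].

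With m = 0, T = 22 and a = 15 this is 1 − (0.5111 − 0.1213)/1.438 = 0.729. Then 150 × 0.729 = 109.4, which matches the stated 110 and leaves no slack.

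**3. Where slack exists.**
- True hazard ratio 1.5, no loss: 118.4 failures at month 22 from 150 patients. About 16% loss per year is tolerated (m = 0.0145).
- Hazard ratio 1.0, 160 patients, no loss: 114.0 at month 22, with the 110th at month 21.1. About 7.5% loss per year is tolerated (m = 0.0065).

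**4. With deaths.** The documents give no survival figure, so a range of medians is assumed, equal by arm, at hazard ratio 1.0. Under independence m = ln 2 / median survival. Example for median 12 and 160 patients: m = 0.0578 and h = 0.1537. The fraction is 0.624 × [1 − (0.3977 − 0.0340)/2.459] = 0.532, or 85 failures. The expected number ever attainable is N·λ/h, and the chance of ever reaching 110 is binomial with p = λ/h.

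Failure may tend to precede death. To represent this, the death hazard is also doubled after failure, with m solved so that overall median survival equals the assumed value.

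Each cell shows 160 patients (150 patients):

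| Assumed median survival, months | 6 | 12 | 18 | 24 |
|---|---|---|---|---|
| Independent: failures at month 22 | 67 (63) | 85 (81) | 93 (89) | 98 (94) |
| Independent: ever attainable | 73 (68) | 100 (94) | 114 (107) | 123 (115) |
| Independent: chance of reaching 110 | <0.1% (<0.1%) | 6% (0.3%) | 79% (33%) | 99% (87%) |
| Doubled: failures at month 22 | 72 (69) | 92 (87) | 99 (95) | 103 (99) |
| Doubled: ever attainable | 80 (75) | 111 (104) | 126 (118) | 134 (126) |
| Doubled: chance of reaching 110 | <0.1% (<0.1%) | 62% (18%) | >99% (96%) | >99% (>99%) |

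**5. Threshold without an independence assumption.** The expected total stays below 110 when m > λ(N/110 − 1). That is 0.044 per month (41% per year) for 160 patients and 0.035 per month (34% per year) for 150. The corresponding median overall survival, for 160 and 150 patients, is:
- about 16 and 20 months under independence;
- 11.6 and 14.0 months if the death hazard doubles after failure;
- 9.9 and 11.7 months if it triples.

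At a true hazard ratio of 1.5 under independence, the thresholds are 13.1 and 16.4 months.

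**6. Power at month 22.** Power = Φ(ln 1.5 × √d / 2 − 0.8416) for d failures. Under independence, medians of 6 to 24 months give 0.79 to 0.88 with 160 patients and 0.78 to 0.87 with 150.

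**The case against.** The strongest objection is about scale. Section 11 words the 25% as a proportion of patients, and its Final Analysis part works with cumulative incidence and a Fine-Gray test. If the exponential curve is itself the cumulative incidence, deaths are already inside it and 109.4 stands apart from loss to follow-up. That reading cannot be excluded. It requires 1 − e^(−12λ) = 68% of patients to have failed by 12 months and 88% by 22 months despite deaths, and the plan does not say this is meant.

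An intermediate reading takes 25% as the 3-month incidence observed with deaths occurring, which makes the failure hazard somewhat higher than 0.0959. For 160 patients under independence, the attainable totals become about 80, 103, 116 and 124 instead of 73, 100, 114 and 123. The change is small.

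Failure includes progression and re-irradiation in Section 9, so it may well precede death. With the death hazard tripled after failure, 160 patients at a 12-month median have about a 94% chance of reaching 110. This stands: whether the trigger would be missed depends on survival and on that relation, and neither is documented. Month 22 is still missed in every scenario in the table.

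The power loss is modest for a screening test at 0.20, an event-driven analysis without a cut-off date is a legitimate choice, and the test may already have been run. All of this is fair. It limits the consequence but does not supply the missing assumption or bound the wait.

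**Conclusion.** The concern holds and should be fixed. At hazard ratio 1.0 the 22-month projection matches a calculation with no death or loss before failure. The plan states no such rate, and the 110th failure is the only trigger for the analysis that gates phase III. Confidence in these points is high, subject to the cumulative-incidence reading.

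Confidence that 110 would actually be missed is medium to low. The shortfall rests on assumed survival, on how death relates to failure, and, for the 160 patients, on accrual at the planned rate. At month 22 it runs from about 43 failures (6-month median, independent) to about 7 (24-month median, death hazard doubled after failure). The type I error rate is not affected. If the test has already been run, only the reporting point remains.

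**What to change.** 1. State the assumed rates of death and loss, and whether the 25% at 3 months is a cumulative incidence with deaths included. Restate expected failures, duration and power on that basis.
2. If the phase II test has not been run, trigger it at 110 failures or a fixed calendar date, whichever comes first. One option is 12 months after the last phase II patient. For 160 patients and median survival of 6, 12, 18 or 24 months, that date gives about 71, 94, 105 or 111 failures and power of 0.81, 0.87, 0.89 or 0.90 under independence. With the death hazard doubled after failure it gives 78, 103, 113 or 119 failures. Accrual dates are not given, so this date may already have passed and another may be needed.
3. If the test has been run, report the number of failures and the analysis date in place of item 2.
4. Add one line stating that the 1.5 margin is a subdistribution hazard ratio, to match the Fine-Gray test.

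The cost is a SAP amendment and no extra patients, since Section 7 already follows patients until death. Stated phase II power may fall somewhat below 0.90. Because 160 patients are already randomized, the date must be chosen blind to outcomes by arm and the choice documented, or it may look data-driven.
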